#### Table 14.2.1 Summary of FIX in plasma - Data from central laboratory - One Stage aPTT assay - FAS

	Cohort 1 (N = x)	Cohort 2 (N = x)	Total (N = x)
Visit 3			
n	х	x	х
Mean (SD)	xx.xx (x.xx)	xx.xx (x.xx)	xx.xx (x.xx)
Median	x.xx	X.XX	x.xx
Min ; Max	x.x ; xx.x	x.x ; xx.x	x.x ; xx.x
CV (%)	XX.X	XX.X	xx.x
Visit 4			
n	x	х	х
Mean (SD)	x.xx ( x.xx)	x.xx ( x.xx)	x.xx ( x.xx)
Median	x.xx	x.xx	X.XX
Min ; Max	x.x ; xx.x	x.x ; xx.x	x.x ; xx.x
CV (%)	xx.x	XX.X	XX.X
Continue until visit 23			

N: Number of patients in Full Analysis Set (FAS). n: Number of patients with the parameter. SD: Standard Deviation. CV: Coefficient of Variation. LLOQ: LLOQ/2.

Cohort 1: AAV5-hFIX 5.0 x 10^12 gc/kg, Cohort 2: AAV5-hFIX 2.0 x 10^13 gc/kg

No adjustment has been performed for time since most recent administration of FIX replacement therapy, which implies some data could be contaminated with exogenous FIX. At Visit 2, Day 1 the pre-challenge dose measurement data are tabulated; the 30-min post challenge dose data are presented in the listings.

Sponsor: uniQure biopharma B.V	D	Date 27MAY2021		larix	
Trial ID: CT-AMT-060-01 EudraCT No: 2013-00557942-42		Table Shells		Final Version 05 Page 14 of 66	
Table 14.2.2 Summary of FIX-replace	able 14.2.2 Summary of EIV replacement thereasy free EIV in placeme. Data from control laboratory. One Stage aBTT access. EAS				
	$\frac{\text{Cohort 1}}{(N = x)}$	Cohort 2 (N = x)	$\frac{\text{Total}}{(N=x)}$	1110	
One-stage aPTT for FIX activity (%)					
Visit 1					
n	х	х	х		
Mean (SD)	x.xx(x.xx)	x.xx(x.xx)	x.xx(x.xx)		
Median	x.xx	X.XX	X.XX		
Min ; Max	x.x; x.x	x.x; x.x	x.x; x.x		
CV (%)	X.X	X.X	X.X		
Visit 2, Day 1					
n	х	х	х		
Mean (SD)	x.xx(x.xx)	x.xx(x.xx)	x.xx(x.xx)		
Median	x.xx	x.xx	X.XX		
Min ; Max	x.x; x.x	x.x; x.x	x.x; x.x		
CV (%)	X.X	X.X	X.X		
Visit 3					
n	х	х	х		
Mean (SD)	x.xx(x.xx)	x.xx(x.xx)	x.xx(x.xx)		
Median	x.xx	x.xx	X.XX		
Min ; Max	x.x; x.x	x.x; x.x	x.x; x.x		
CV (%)	X.X	X.X	X.X		
Continue until visit 26					

N: Number of patients in Full Analysis Set (FAS). n: Number of patients with the parameter. SD: Standard Deviation. CV: Coefficient of Variation. LLOQ: LLOQ/2.

Cohort 1: AAV5-hFIX 5.0 x 10^12 gc/kg, Cohort 2: AAV5-hFIX 2.0 x 10^13 gc/kg

Only assessments performed more than 10 days after most recent FIX-replacement therapy administration included.

At Visit 2, Day 1 the pre-challenge dose measurement data are tabulated; the 30-min post challenge dose data are presented in the listings.

Sponsor: uniQure biopharma B.V	ſ	Date 27MAY2021		larix
Trial ID: CT-AMT-060-01 EudraCT No: 2013-00557942-42		Table Shells		Final Version 05 Page 15 of 66
Table 14.2.3 Summary of FIX in plasma - I	Data from central labora	atory - Chromogenic/Amidolytic	assay - FAS	
	Cohort 1 (N = x)	Cohort 2 (N = x)	Total (N = x)	
Chromogenic/amidolytic assay for FIX activity (%)				
Visit 1				
n	х	x	х	
Mean (SD)	x.xx(x.xx)	x.xx(x.xx)	x.xx(x.xx)	
Median	x.xx	X.XX	X.XX	
Min ; Max	x.x; x.x	x.x; x.x	x.x; x.x	
CV (%)	x.x	X.X	X.X	
Visit 2, Day 1, Pre-dose				
n	х	х	х	
Mean (SD)	x.xx(x.xx)	x.xx(x.xx)	x.xx(x.xx)	
Median	x.xx	x.xx	x.xx	
Min ; Max	x.x; x.x	x.x; x.x	x.x; x.x	
CV (%)	x.x	X.X	X.X	
Visit 2, Day 1				
n	х	x	х	
Mean (SD)	x.xx(x.xx)	x.xx(x.xx)	x.xx(x.xx)	
Median	x.xx	X.XX	x.xx	
Min ; Max	x.x; x.x	x.x; x.x	x.x; x.x	
CV (%)	x.x	X.X	X.X	
Continue until visit 26				

N: Number of patients in Full Analysis Set (FAS). n: Number of patients with the parameter. SD: Standard Deviation. CV: Coefficient of Variation. LLOQ: LLOQ/2.

Cohort 1: AAV5-hFIX 5.0 x 10^12 gc/kg, Cohort 2: AAV5-hFIX 2.0 x 10^13 gc/kg

No adjustment has been performed for time since most recent administration of FIX replacement therapy, which implies some data could be contaminated with exogenous FIX.

At Visit 2, Day 1 the pre-challenge dose measurement data are tabulated; the 30-min post challenge dose data are presented in the listings.

Sponsor: uniQure biopharma B.V	Date 27MAY2021	larix
Trial ID: CT-AMT-060-01 EudraCT No: 2013-00557942-42	Table Shells	Final Version 05 Page 16 of 66

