Weeks ²⁾	39	52 (1 year)	65, 78, 91	104 (2 years)	117, 130, 143	156 (3 years)	182	208 (4 years)	234		260 (5 years)
Visit window ²⁾	±2 weeks	±2 weeks	±2 weeks	±2 weeks	±2 weeks	±2 weeks	±4 weeks	±4 weeks	±4 weeks		±4 weeks
Local Laboratory											
FIX: one-stage aPTT or chromogenic/amidolytic assay for FIX activity for local monitoring ⁵⁾	x	x	x	x	x	x	x	x	x	(x) ¹⁾	x
FIX inhibitors (Bethesda assay or Nijmegen modified Bethesda assay) for local monitoring and eligibility check ³⁾		x		x		x		x		(x) ¹⁾	x
Liver enzymes (AST/ALT)										(x) ¹⁾	
Central Laboratory											
FIX: one-stage aPTT and chromogenic/amidolytic assay for FIX activity, and FIX protein concentration	x	x	x	x	x	x	x	x	x	(x) ¹⁾	x
Anti-FIX antibodies		x		x		x		x			x
FIX inhibitors (Nijmegen modified Bethesda assay)		x		x		x		x		(x) ¹⁾	x
FIX recovery ⁴⁾										(x) ¹⁾	
Total (IgM and IgG) antibodies to AAV5		x		x		x		x			x
Neutralizing antibodies to AAV5		x		x		x		x			x
Sampling for vector genome detection: Blood, urine, saliva, nasal secretions ⁵⁾	x	x	x	x	x	x	x	x	x		x
Faeces, semen ⁵⁾	x	x	x	x	x	x	x	x	x		x
Haematology parameters ⁶⁾	x	x	x	x	x	x	x	x	x	(x) ¹⁾	x
Coagulation parameters ⁷⁾	x	x	x	x	x	x	x	x	x	(x) ¹⁾	x
Serum chemistry parameters ⁸⁾	x	x	x	x	x	x	x	x	x	(x) ¹⁾	x
Urine parameters ⁹⁾	x	x	x	x	x	x	x	x	x	(x) ¹⁾	x
Blood sample for future research ¹⁰⁾		x									

Footnotes are given on next page.

Clinical Trial Protocol

Trial ID: CT-AMT-060-01

Footnotes to [Table 5-5](#):

- 1) An additional visit can be performed at any time for the purpose of conducting one or more procedures listed in the column "Additional Visits" according to the choice of the Investigator. Hence, "(x)" refers to a procedure that can be performed, if judged relevant by the Investigator.
- 2) Each visit and time point is scheduled in relation to date of IMP administration, not in relation to the date of its previous visit or time point.
- 3) Preferably, the same type of assay is used consistently for the individual subject throughout the entire trial period.
- 4) At suspicion of FIX inhibitor or at increase in bleeding frequency, as judged by the Investigator. At each occasion a FIX challenge dose of 40 U/kg should be administered. A blood sample should be drawn just prior FIX dosing and at 30 minutes after FIX dosing.

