## 4.4.2 Secondary Efficacy Analyses

#### 4.4.2.1 FIX Levels in Plasma

Blood samples for FIX activity will be collected at all visits. At Visit 2, blood sampling will take place prior to IMP administration.

Throughout the entire trial period (from Visit 1 and onwards) where a patient is on prophylactic FIX replacement therapy, it will be the aim to draw blood samples at time points where FIX activity is expected to be at the lowest levels. To the extent the visit windows allow, the investigator and/or study nurse will collaborate with the patient to schedule visits to take place on days where prophylactic FIX replacement therapy is planned to be administered. At these visits, blood sampling will then take place just prior to administration of prophylactic FIX replacement therapy.

The following FIX activity assays will be applied at the central laboratory:

- one-stage aPTT assay
- chromogenic/amidolytic assay

The data will be presented separately for each activity assay.

Absolute values will be listed and for each measurement the number of days since last FIX replacement therapy administration will be displayed.

The data will also be analysed descriptively by visit and cohort. These summaries will be generated both for a) all FIX measurements data b) FIX-replacement therapy free FIX measurements i.e. only measurement taken more than 10 days after the preceding FIX replacement therapy administration are included.

The procedure for calculating the above distance and defining latest FIX replacement therapy administration preceding the FIX activity measurement in question has been described in section 4.1. It is noted that if the date for a FIX replacement therapy administration is identical to the date of a FIX activity measurement and no time is indicated, then the FIX activity measurement in question is conservatively assumed to be contaminated i.e. as not FIX-replacement therapy free (the distance between the two time points will be calculated to 1 day).

For the one-stage aPTT assay data the patient individual profiles of FIX replacement free measurements in the period from last prophylactic dose (after tapering) until cut-off will also be presented. Regression lines will be presented and 95% confidence intervals will be displayed as part of legend for each patient.

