## 4.4.2.2 Number, Severity and Type of Bleeding Episodes

In relation to the efficacy variables defined in this section and in section 4.4.2.3 a specific subset of the post-treatment period will be considered.

Larix A/S - Strictly Confidential F501-0-1–5 SAP Template Page 17 of 34 Date: 27MAY2021

Final no. 05

Page 18 of 34

CT-AMT-060-01 EudraCT No.: 2013-005579-42 Statistical Analysis Plan

For the interim analyses described in section 5 the end of this specific post treatment will simply be the specified cut-off date. For the final analysis, this will be the end of study date.

The start of this period is defined for each patient as the end of tapering, i.e. the date of the last prophylactic FIX replacement therapy administered. Before the data base freeze for an interim analysis in question (c.f. section 5) this start date will be decided on for each patient. The decisions made in connections with the first formal interim analysis (c.f. section 5) appear in Appendix 2.

As mentioned in section 4.3.4.3 all bleeding episodes occurring in the one year period prior to screening will be registered.

These data will be presented in a listing and also summarized with respect to annualized bleeding rate, and number of episodes. Separate summaries will be generated for all bleeds and for the different types of bleeds (spontaneous, traumatic, unknown, spontaneous+unknown). It is assumed that the bleeding episodes are observed during exactly one year i.e. the observed number bleeds will correspond exactly to the annualized bleeding rate for the 1 year prior to screening data for each patient.

From Visit 1 and throughout the entire trial participation period, patients will be asked to record information on bleeding episodes in an e-diary.

The patient e-diary will include questions regarding each bleeding episode with respect to

- Date and time of onset of bleed
- Date and time of stop of bleed
- Location of bleed (a number of categories have been defined in e-diary/eCRF)
- Circumstances of bleed (spontaneous, traumatic, minor surgery see definitions in protocol section 12.12)
- FIX replacement treatment of bleed (medication, dose, date and time of administration)
- Other therapy (pain relieving medication compression, ice)
- Investigator's evaluation of severity of bleed
- Evaluation of effect of treatment by patient (excellent, good, moderate, none), see definitions in protocol section 12.1.2)

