#### Second formal interim analysis:

When all enrolled patients have been followed for at least 52 weeks after the IMP administration, i.e. all enrolled patients have attended Visit 23, another formal data base freeze will be performed for the data base including creation of time-stamped SAS datasets in CDISC SDTM. The data will have the status as "clean data and signed by investigator".

The procedures and analyses to be performed will otherwise be as described for the first interim analysis. After the second interim analysis, an interim report will be written by the sponsor.

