# 7 Tables, Listings and Figures

The shell listings, tables, and figures generated appear in the two shell documents (CT\_AMT\_060\_01\_Table\_Shells\_v05.docx and CT\_AMT\_060\_01\_Listing\_Shells\_v05.docx) attached to this SAP. The two documents are considered as being a part of this SAP.

Larix A/S - Strictly Confidential F501-0-1–5 SAP Template Page 30 of 34

Date: 27MAY2021

CT-AMT-060-01 EudraCT No.: 2013-005579-42

Statistical Analysis Plan

Final no. 05 Page 31 of 34

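### The version 05 table shells end the FIX activity summaries at Visit 23 or Visit 26, but SAP 4.4.2.1 asks for summaries by visit with no last visit and follow-up runs to Visit 35

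*SAP*

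**What the plan says.** On the summaries, SAP 4.4.2.1 states: "The data will also be analysed descriptively by visit and cohort". It wants them separately for the one-stage and chromogenic assays, and both for all measurements and for replacement-therapy-free measurements. The same section says FIX activity is sampled at every visit. It names no visit at which the summaries end.

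The shells do name one. Table 14.2.1 (one-stage, all measurements) has "Continue until visit 23". Tables 14.2.2 (one-stage, replacement-therapy-free), 14.2.3 (chromogenic, all) and 14.2.4 (chromogenic, replacement-therapy-free) have "Continue until visit 26".

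The shells have the same standing as the text. SAP section 7 says of the table and listing shells: "The two documents are considered as being a part of this SAP". They are headed final version 05 and dated 27 May 2021, the date of SAP edition 05.

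The SAP covers the final analysis as well as the interims. SAP 4.4.2.2 defines the end of the post-tapering period for bleeding and FIX use and adds: "For the final analysis, this will be the end of study date". Protocol 20.1 requires all safety and efficacy data to be locked, analysed and reported after Visit 35. Protocol Table 5-5 schedules "FIX: one-stage aPTT and chromogenic/amidolytic assay for FIX activity, and FIX protein concentration" at the central laboratory at every visit from 22 to 35.

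**The concern.** One SAP gives two different instructions for the same four tables. In the text available, nothing says whether the section text or the shells prevail. The shells also disagree with each other: the measurements in Table 14.2.2 are a subset of those in Table 14.2.1, yet Table 14.2.2 runs to a later visit.

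The endpoint affected is replacement-therapy-free FIX activity, the only efficacy endpoint labelled confirmatory (Protocol 8.2.2; SAP 1.2). Whether expression lasts is central for a single-dose gene therapy followed for five years; Protocol 6.7 describes the aim as expression that is both stable and durable. If the shells are followed, no cohort summary of this endpoint exists after week 91.

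What remains for the later years differs by assay. SAP 4.4.2.1 continues: "For the one-stage aPTT assay data the patient individual profiles of FIX replacement free measurements in the period from last prophylactic dose", with regression lines and a 95% confidence interval for each patient, up to the cut-off. That is for the one-stage assay only. After week 91 the chromogenic assay would have listings alone.

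**Working it through.** No power or sample-size figure is involved. The check sets the shells against the visit schedule.

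**Inputs**
- Central FIX activity after dosing (Protocol Tables 5-2 and 5-5): Visits 3-14, 15-20, 21 and 22-35. The extra weekly visits 3b-14b are local-laboratory only for FIX and are not counted.
- Number of visits: 12 + 6 + 1 + 14 = 33.
- Weeks of Visits 22-35 (Protocol Tables 5-4 and 5-5): 39, 52, 65, 78, 91, 104, 117, 130, 143, 156, 182, 208, 234, 260. So Visit 23 is week 52, Visit 26 is week 91 and Visit 35 is week 260.

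**Coverage if the shells are followed**

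| Shell | Content | Last visit (week) | Visits omitted | Follow-up after last visit |
|---|---|---|---|---|
| 14.2.1 | One-stage, all | 23 (52) | 24-35: 12/33 = 36% | (260 - 52)/260 = 208/260 = 80% |
| 14.2.2 | One-stage, replacement-free | 26 (91) | 27-35: 9/33 = 27% | (260 - 91)/260 = 169/260 = 65% |
| 14.2.3 | Chromogenic, all | 26 (91) | 9/33 = 27% | 65% |
| 14.2.4 | Chromogenic, replacement-free | 26 (91) | 9/33 = 27% | 65% |

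**Annual time points.** These are Visits 23, 27, 31, 33 and 35 (weeks 52, 104, 156, 208 and 260). Only Visit 23 falls within either limit, so all four tables omit 4 of 5.

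**Disagreement between shells.** Table 14.2.2 minus Table 14.2.1 is Visits 24, 25 and 26 (weeks 65, 78 and 91): three visits at which the subset would be summarised but the full set would not.

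**Can the stops be read as interim limits?** SAP section 5 triggers the first formal interim when all patients have completed Visit 14, and the second when "all enrolled patients have attended Visit 23". Visit 26 is neither of these milestones and is not the final visit. No wording confines these four shells to an interim. Shell Table 14.1.1 has a row for study completers, which points to final use. Some shell footers still carry a January 2018 date. This pattern fits shells that were reissued in 2021 without being extended.

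**The case against.** The strongest reply is that the harm is conditional and the governing text points one way. SAP 4.4.2.1, Protocol 14.2.2 (summary tables by time point and dose level) and Protocol 20.1 all lead to summaries through Visit 35. Against them stands only a layout note in a mock table, and a careful programmer would probably run the tables to the end. This is true. It is why the point is a correction that should be made and not a fatal flaw. But section 7 gives the layout note the status of SAP text, so the choice should not be left to the programmer.

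Second, Visit 26 may have an innocent origin. The interims used calendar cut-offs (SAP Appendix 1: 5 August 2016 and 12 May 2017), so patients dosed early would have visits beyond 23 at the second cut-off. Dosing dates are not in the documents. On the assumption that the first patient was dosed between about mid-May and mid-August 2015, Visit 26 would be the latest visit reached by 12 May 2017 (week 91 reached, week 104 not). This may well be right. It explains where the note came from, but it does not make the note suitable for a five-year report.

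Third, cohorts are small (5 to 7 patients), every value is listed with days since the last FIX dose, the one-stage profiles carry regression lines and intervals, and no hypothesis is tested (SAP 4.1). So no inference changes and a reader could rebuild the summaries. That stands and limits the severity. The 65% and 80% figures are calendar time; the shares of scheduled visits omitted are 27% and 36%.

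Finally, the body of SAP 4.7, on assigning visits, is not in the text available. It could bear on which visit a value belongs to; whether it touches the end of these tables cannot be seen.

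**Conclusion.** The conflict is real. As written, the shells stop the FIX activity tables at week 91 (week 52 for Table 14.2.1) in a SAP that also governs the five-year analysis, and the SAP's own text sets no such stop. The sizes tabulated above apply only if the shells, and not SAP 4.4.2.1, are followed; if the text is followed, nothing is missing. The visit counts rest on the scheduled main visits and take no account of missed or additional visits. Outdated shells are the likely cause, but that is inference. The point should be corrected; it does not call the data or the rest of the analysis into question.

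**What to change.** Change the closing note in shells 14.2.1, 14.2.2, 14.2.3 and 14.2.4 so that each table continues to Visit 35. Each would then cover all 33 post-dose visits: Table 14.2.1 gains 12 and the other three gain 9 each. If the final tables already exist, confirm that they ran to Visit 35 and record it.

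While making the edit:
- State whether values taken at an early end-of-trial visit enter the Visit 35 row. Protocol 9.4 calls withdrawing patients in for Visit 35 procedures, so such values are not necessarily five-year values.
- Check the other shells for the same pattern. Table 14.2.20 shows only Visits 1, 21 and 23, although SAP 4.4.2.4 asks for summaries by visit and Protocol 10.2.3 continues the questionnaire to Visit 35. The post-baseline joint listings are titled for week 52 only.
- As a separate minor correction, reconcile the joint-status visits in SAP 4.6.7 (21, 23, 25, 27, 29 and 31-35) with Protocol 12.3.7 (23, 27, 31, 33 and 35).

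The cost is four shell notes for the main point, plus a line of SAP text for the joint-status visits and small edits for anything else the check turns up. No new data or statistical method is needed, because central FIX activity is already sampled at every visit to Visit 35.

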#### Table 14.2.4 Summary of FIX-replacement-therapy-free FIX in plasma - Data from central laboratory - Chromogenic/Amidolytic assay - FAS

	Cohort 1 (N = x)	Cohort 2 (N = x)	Total (N = x)	
Chromogenic/amidolytic assay for FIX activity (	%)			
Visit 1				
n	х	х	х	
Mean (SD)	x.xx(x.xx)	x.xx(x.xx)	x.xx(x.xx)	
Median	x.xx	x.xx	X.XX	
Min ; Max	x.x; x.x	x.x; x.x	x.x; x.x	
CV (%)	X.X	X.X	X.X	
Visit 2, Day 1				
n	х	х	х	
Mean (SD)	x.xx(x.xx)	x.xx(x.xx)	x.xx(x.xx)	
Median	X.XX	x.xx	X.XX	
Min ; Max	x.x; x.x	x.x; x.x	x.x; x.x	
CV (%)	X.X	X.X	X.X	
Continue until visit 26				

N: Number of patients in Full Analysis Set (FAS). n: Number of patients with the parameter. SD: Standard Deviation. CV: Coefficient of Variation. LLOQ: LLOQ/2.

Cohort 1: AAV5-hFIX 5.0 x 10^12 gc/kg, Cohort 2: AAV5-hFIX 2.0 x 10^13 gc/kg

Only assessments performed more than 10 days after most recent FIX-replacement therapy administration included.

At Visit 2, Day 1 the pre-challenge dose measurement data are tabulated; the 30-min post challenge dose data are presented in the listings.

Sponsor: uniQure biopharma B.V		Date 27MAY2021		larix
Trial ID: CT-AMT-060-01 EudraCT No: 2013-00557942-42		Table Shells		Final Version 05 Page 17 of 66
Table 14.2.5 Summary of pre-treatment	use of FIX replacen	nent therapy - On-Dema	nd - Period: One year prior to screening - FAS	
	Cohort 1 (N=x)	Cohort 2 (N=x)	Total (N=x)	
Use of on-demand FIX replacement therapy	n (%)	n (%)	n (%)	
Any medication	x (xx.x)	x (xx.x)	x (xx.x)	
Benefix	x (xx.x)	x (xx.x)	x (xx.x)	
Haemonine	x (xx.x)	x (xx.x)	x (xx.x)	
Mononine	x (xx.x)	x (xx.x)	x (xx.x)	
Etc.				
Repeat for all medications reported				

N: Number of patients in Full Analysis Set (FAS). n: Number of patients with at least one dose of medication. Cohort 1: AAV5-hFIX 5.0 x 10^12 gc/kg, Cohort 2: AAV5-hFIX 2.0 x 10^13 gc/kg

Sponsor: uniQure biopharma B.V		Date 27MAY2021		larix
Trial ID: CT-AMT-060-01 EudraCT No: 2013-00557942-42		Table Shells		Final Version 05 Page 18 of 66
Table 14.2.6 Summary of post-treatment	use of FIX replace	ment therapy - Prophyla	xis - Period: From Dosing To cut-off - FAS	
Use of prophylactic FIX replacement therapy	Cohort 1 (N=x) n (%)	Cohort 2 (N=x) n (%)	Total (N=x) n (%)	
Any medication	x (xx.x)	x (xx.x)	x (xx.x)	
Benefix	x (xx.x)	x (xx.x)	x (xx.x)	
Haemonine	x (xx.x)	x (xx.x)	x (xx.x)	
Mononine	x (xx.x)	x (xx.x)	x (xx.x)	
Etc.				
Repeat for all medications reported				

N: Number of patients in Full Analysis Set (FAS). n: Number of patients with at least one dose of medication. Cohort 1: AAV5-hFIX 5.0 x 10^12 gc/kg, Cohort 2: AAV5-hFIX 2.0 x 10^13 gc/kg

Sponsor: uniQure biopharma B.V		Date 27MAY2021		larix
Trial ID: CT-AMT-060-01 EudraCT No: 2013-00557942-42		Table Shells		Final Version 05 Page 19 of 66
Table 14.2.7 Summary of post-treatment	t use of FIX replace	ment therapy - On-Dema	and - Period: From Dosing To cut	-off - FAS
	Cohort 1 (N=x)	Cohort 2 (N=x)	Total (N=x)	
Use of on-demand FIX replacement therapy	n (%)	n (%)	n (%)	
Any medication	x (xx.x)	x (xx.x)	x (xx.x)	
Benefix	x (xx.x)	x (xx.x)	x (xx.x)	
Haemonine	x (xx.x)	x (xx.x)	x (xx.x)	
Mononine	x (xx.x)	x (xx.x)	x (xx.x)	
Etc.				
Repeat for all medications reported				

N: Number of patients in Full Analysis Set (FAS). n: Number of patients with at least one dose of medication. Cohort 1: AAV5-hFIX 5.0 x 10^12 gc/kg, Cohort 2: AAV5-hFIX 2.0 x 10^13 gc/kg

Sponsor: uniQure biopharma B.V		Date 27MAY2021		larix
Trial ID: CT-AMT-060-01 EudraCT No: 2013-00557942-42		Table Shells		Final Version 05 Page 20 of 66
Table 14.2.8 Summary o	f FIX replacement therapy d	lose - Period: One year prior t	o screening - FAS	
	Cohort 1 (N=x)	Cohort 2 (N=x)	Total (N=x)	
FIX Infusions (IU/year)				
n	x	x	x	
Mean (SD)	xxx (xxx)	xxx (xxx)	xxx (xxx)	
Median	XXX	XXX	XXX	
Min ; Max	xxx ; xxx	xxx ; xxx	xxx ; xxx	

N: Number of patients in Full Analysis Set (FAS). n: Number of patients with at least one dose of medication. Cohort 1: AAV5-hFIX 5.0 x 10^12 gc/kg, Cohort 2: AAV5-hFIX 2.0 x 10^13 gc/kg FIX infusions is the total sum of FIX administrated as prophylaxis and On-demand.

Sponsor: uniQure biopharma B.V		Date 27MAY2021		larix
Trial ID: CT-AMT-060-01 EudraCT No: 2013-00557942-42		Table Shells		Final Version 05 Page 21 of 66
Table 14.2.9 Summary of	FIX replacement therapy d	lose - Period: From tapering-o	ff to cut-off - FAS	
	Cohort 1 (N=x)	Cohort 2 (N=x)	Total (N=x)	
Annualized FIX Infusions (IU/yea	r)			
n	х	x	х	
Mean (SD)	xxx (xxx)	xxx (xxx)	xxx (xxx)	
Median	XXX	XXX	XXX	
Min ; Max	xxx ; xxx	xxx ; xxx	xxx ; xxx	

N: Number of patients in Full Analysis Set (FAS). n: Number of patients with at least one dose of medication. Cohort 1: AAV5-hFIX 5.0 x 10^12 gc/kg, Cohort 2: AAV5-hFIX 2.0 x 10^13 gc/kg FIX infusions is the total sum of FIX administrated as prophylaxis and On-demand.

Sponsor: uniQure biopharma B.V	Date 27MAY2021			larix
Trial ID: CT-AMT-060-01 EudraCT No: 2013-00557942-42	Та	able Shells		Final Version 05 Page 22 of 66
Table 14.2.10 Summary of bleeding episode	s and annualized bleedin	g rates - All bleeds - Per	iod: One year prior to screening - FAS	6
	Cohort 1 (N=x) n (%)	Cohort 2 (N=x) n (%)	Total (N=x) n (%)	
Number of patients with bleed, n (%)	x (xx.x)	x (xx.x)	x (xx.x)	
Number of bleeds	x	x	x	
Bleeds per patient (min; max)	x; x	x; x	x; x	
Annualized bleeding rate				
n	х	х	x	
Mean (SD)	x.xx (x.xx)	x.xx (x.xx)	x.xx (x.xx)	
Median	x.xx	x.xx	X.XX	
Min ; Max	x.x; x.x	x.x; x.x	x.x; x.x	

N: Number of patients in Full Analysis Set (FAS). n: Number of patients with the parameter. SD: Standard Deviation. n\*: Number of bleeds. Severity: Assessment by investigator.

Cohort 1: AAV5-hFIX 5.0 x 10^12 gc/kg, Cohort 2: AAV5-hFIX 2.0 x 10^13 gc/kg

Only bleeds requiring on demand FIX infusion are included.

Sponsor: uniQure biopharma B.V	Date		larix	
Trial ID: CT-AMT-060-01 EudraCT No: 2013-00557942-42	Та	ble Shells		Final Version 05 Page 23 of 66
Table 14.2.11 Summary of bleeding episodes	and annualized bleeding	g rates - Spontaneous ble	eeds - Period: One year prior to screen	ing - FAS
_	Cohort 1 (N=x) n (%)	Cohort 2 (N=x) n (%)	Total (N=x) n (%)	
Number of patients with bleed, n (%)	x (xx.x)	x (xx.x)	x (xx.x)	
Number of bleeds	х	х	х	
Bleeds per patient (min; max)	x; x	x; x	x; x	
Annualized bleeding rate				
n	х	х	x	
Mean (SD)	x.xx (x.xx)	x.xx (x.xx)	x.xx (x.xx)	
Median	X.XX	x.xx	X.XX	
Min ; Max	x.x; x.x	x.x; x.x	x.x; x.x	

N: Number of patients in Full Analysis Set (FAS). n: Number of patients with the parameter. SD: Standard Deviation. n\*: Number of bleeds. Severity: Assessment by investigator.

Cohort 1: AAV5-hFIX 5.0 x 10^12 gc/kg, Cohort 2: AAV5-hFIX 2.0 x 10^13 gc/kg

Only bleeds requiring on demand FIX infusion are included.

Sponsor: uniQure biopharma B.V	Date 27MAY2021			larix
Trial ID: CT-AMT-060-01 EudraCT No: 2013-00557942-42	Та	ble Shells		Final Version 05 Page 24 of 66
Table 14.2.12 Summary of bleeding episodes	and annualized bleeding	g rates - Traumatic bleed	ds - Period: One year prior to screening	- FAS
	Cohort 1 (N=x) n (%)	Cohort 2 (N=x) n (%)	Total (N=x) n (%)	
Number of natients with bleed n (%)	x (xx x)	x (xx x)	x (xx x)	
Number of bleeds	X	X	x	
Bleeds per patient (min; max)	x; x	x; x	x; x	
Annualized bleeding rate				
n	х	х	x	
Mean (SD)	x.xx (x.xx)	x.xx (x.xx)	x.xx (x.xx)	
Median	x.xx	x.xx	X.XX	
Min ; Max	x.x; x.x	x.x; x.x	x.x; x.x	

N: Number of patients in Full Analysis Set (FAS). n: Number of patients with the parameter. SD: Standard Deviation. n\*: Number of bleeds. Severity: Assessment by investigator.

Cohort 1: AAV5-hFIX 5.0 x 10^12 gc/kg, Cohort 2: AAV5-hFIX 2.0 x 10^13 gc/kg

Only bleeds requiring on demand FIX infusion are included.

Sponsor: uniQure biopharma B.V	Date 27MAY2021			arix
Trial ID: CT-AMT-060-01 EudraCT No: 2013-00557942-42	-	Table Shells	Fina P	al Version 05 age 25 of 66
Table 14.2.13 Summary of bleeding episode	s and annualized bleeding	ng rates - Unknown bleed	ds - Period: One year prior to screening - FA	AS
	Cohort 1 (N=x) n (%)	Cohort 2 (N=x) n (%)	Total (N=x) n (%)	
Number of nations with bleed n (%)	y ( yy y )	y (yy y)	x (yy y)	
Number of bleeds	X	X	X (AA.A)	
Bleeds per patient (min; max)	x; x	x; x	x; x	
Annualized bleeding rate				
n	х	х	x	
Mean (SD)	x.xx (x.xx)	x.xx (x.xx)	x.xx (x.xx)	
Median	x.xx	x.xx	X.XX	
Min ; Max	x.x; x.x	x.x; x.x	x.x; x.x	

N: Number of patients in Full Analysis Set (FAS). n: Number of patients with the parameter. SD: Standard Deviation. n\*: Number of bleeds. Severity: Assessment by investigator.

Cohort 1: AAV5-hFIX 5.0 x 10^12 gc/kg, Cohort 2: AAV5-hFIX 2.0 x 10^13 gc/kg

Only bleeds requiring on demand FIX infusion are included.

Sponsor: uniQure biopharma B.V	Date 27MAY2021	larix
Trial ID: CT-AMT-060-01 _EudraCT No: 2013-00557942-42	Table Shells	Final Version 05 Page 26 of 66

Table 14.2.14 Summary of bleeding episodes and annualized bleeding rates - Spontaneous and unknown bleeds - Period: One year prior to screening - FAS

	Cohort 1 (N=x) n (%)	Cohort 2 (N=x) n (%)	Total (N=x) n (%)
Number of patients with bleed, n (%)	x (xx.x)	x (xx.x)	x (xx.x)
Number of bleeds	х	х	x
Bleeds per patient (min; max)	x; x	x; x	х; х
Annualized bleeding rate			
n	х	х	x
Mean (SD)	x.xx (x.xx)	x.xx (x.xx)	x.xx (x.xx)
Median	x.xx	x.xx	x.xx
Min ; Max	x.x; x.x	x.x; x.x	X.X; X.X

N: Number of patients in Full Analysis Set (FAS). n: Number of patients with the parameter. SD: Standard Deviation. n\*: Number of bleeds.

Severity: Assessment by investigator.

Cohort 1: AAV5-hFIX 5.0 x 10^12 gc/kg, Cohort 2: AAV5-hFIX 2.0 x 10^13 gc/kg

Only bleeds requiring on demand FIX infusion are included.

Sponsor: uniQure biopharma B.V	Date 27MAY2021			larix
Trial ID: CT-AMT-060-01 EudraCT No: 2013-00557942-42	т	able Shells		Final Version 05 Page 27 of 66
Table 14.2.15 Summary of bleeding episode	s and annualized bleedin	g rates - All bleeds - Per	riod: From tapering-off to cut-off - FAS	3
	Cohort 1 (N=x) n (%)	Cohort 2 (N=x) n (%)	Total (N=x) n (%)	
Number of patients with bleed, n (%)	x (xx.x)	x (xx.x)	x (xx.x)	
Number of bleeds	xx	XX	xx	
Bleeds per patient (min; max)	x ; x	x ; x	x ; x	
Mean observation period (days)	xxx	xxx	xxx	
Total observation period (days)	xxx	XXX	XXX	
Annualized bleeding rate				
n	x	x	x	
Mean (SD)	x.xx (x.xx)	x.xx (x.xx)	x.xx (x.xx)	
Median	x.xx	x.xx	X.XX	
Min ; Max	x.x ; x.x	x.x ; x.x	x.x ; x.x	

N: Number of patients in Full Analysis Set (FAS). n: Number of patients with the parameter. SD: Standard Deviation. n\*: Number of bleeds.

Severity: Assessment by investigator.

Cohort 1: AAV5-hFIX 5.0 x 10^12 gc/kg, Cohort 2: AAV5-hFIX 2.0 x 10^13 gc/kg

Only bleeds requiring on demand FIX infusion are included.

Total observation period (yrs) for each cohort is calculated as the sum of the observation periods of all patients in that cohort.

Sponsor: uniQure biopharma B.V	Date 27MAY2021			larix
Trial ID: CT-AMT-060-01 EudraCT No: 2013-00557942-42		Table Shells		Final Version 05 Page 28 of 66
Table 14.2.15 Summary of bleeding episodes and	annualized bleeding rates - All bl	eeds - Period: From tapering-of	f to cut-off - FAS	
	Cohort 1 (N=x) n (%)	Cohort 2 (N=x) n (%)	Total (N=x) n (%)	
Severity, n*				
Severe	х	х	х	
Mild/Moderate	х	х	х	
Location, n*				
Right - Joint, Ankle	х	х	х	
Right - Joint, Elbow	Х	х	x	
Right - Joint, Finger(S)	х	х	х	
Right - Joint, Knee	х	х	х	
Right - Joint, Toe(S)	х	х	х	
Right - Joint, Wrist	х	х	х	
Right - Muscle, Hip, Leg Or Foot	х	х	х	
Left - Joint, Elbow	Х	х	x	
Left - Joint, Knee	Х	х	Х	
Continued for left	х	х	х	
Muscle, Back Incl Buttocks	х	х	х	
Other	х	х	х	

N: Number of patients in Full Analysis Set (FAS). n: Number of patients with the parameter. SD: Standard Deviation. n\*: Number of bleeds.

Severity: Assessment by investigator.

Cohort 1: AAV5-hFIX 5.0 x 10^12 gc/kg, Cohort 2: AAV5-hFIX 2.0 x 10^13 gc/kg

Only bleeds requiring on demand FIX infusion are included.

Total observation period (yrs) for each cohort is calculated as the sum of the observation periods of all patients in that cohort.

Sponsor: uniQure biopharma B.V Trial ID: CT-AMT-060-01	Da	Larix	
EudraCT No: 2013-00557942-42		Table Shells	Page 29 of 66
Table 14.2.16 Summary of bleeding episode	s and annualized bleedi	ng rates - Spontaneous b	leeds - Period: From tapering-off to cut-off - FAS
	Cohort 1 (N=x) n (%)	Cohort 2 (N=x) n (%)	Total (N=x) n (%)
Number of patients with bleed, n (%)	x (xx.x)	x (xx.x)	x (xx.x)
Number of bleeds	х	х	x
Bleeds per patient (min; max)	x ; x	x ; x	x ; x
Mean observation period (days)	xxx	xxx	XXX
Total observation period (days)	XXX	XXX	XXX
Annualized bleeding rate			
n	х	х	x
Mean (SD)	x.xx (x.xx)	x.xx (x.xx)	x.xx (x.xx)
Median	X.XX	X.XX	X.XX
Min ; Max	x.x ; x.x	x.x ; x.x	x.x ; x.x

N: Number of patients in Full Analysis Set (FAS). n: Number of patients with the parameter. SD: Standard Deviation. n\*: Number of bleeds.

Severity: Assessment by investigator.

Cohort 1: AAV5-hFIX 5.0 x 10^12 gc/kg, Cohort 2: AAV5-hFIX 2.0 x 10^13 gc/kg

Only bleeds requiring on demand FIX infusion are included.

Total observation period (yrs) for each cohort is calculated as the sum of the observation periods of all patients in that cohort.

Sponsor: uniQure biopharma B.V	Date 27MAY2021	larix
Trial ID: CT-AMT-060-01 EudraCT No: 2013-00557942-42	Table Shells	Final Version 05 Page 30 of 66

Table 14.2.16 Summary of post treatment bleeding episodes and annualized bleeding rates - Period: From last prophylactic dose to cut-off - Spontaneous bleeds - FAS

	Cohort 1 (N=x)	Cohort 2 (N=x)	Total (N=x)	
	n (%)	n (%)	n (%)	
Severity, n*				
Severe	х	х	x	
Mild/Moderate	х	х	Х	
Location, n*				
Right - Joint, Elbow	х	х	х	
Right - Joint, Finger(S)	х	х	х	
Right - Joint, Knee	х	х	х	
Right - Joint, Wrist	х	х	х	
Left - Joint, Elbow	х	х	х	
Continued for left	х	х	х	
Other	х	х	х	

N: Number of patients in Full Analysis Set (FAS). n: Number of patients with the parameter. SD: Standard Deviation. n\*: Number of bleeds. Severity: Assessment by investigator. Cohort 1: AAV5-hFIX 5.0 x 10^12 gc/kg, Cohort 2: AAV5-hFIX 2.0 x 10^13 gc/kg

Only bleeds requiring on demand FIX infusion are included.

Total observation period (yrs) for each cohort is calculated as the sum of the observation periods of all patients in that cohort.

Sponsor: uniQure biopharma B.V Trial ID: CT-AMT-060-01 EudraCT No: 2013-00557942-42	Date 27MAY2021			
Table 14.2.17 Summary of bleeding episode	s and annualized bleedi	ng rates - Traumatic blee	ds - Period: From tapering-off to cut-off - FAS	
	Cohort 1 (N=x) n (%)	Cohort 2 (N=x) n (%)	Total (N=x) n (%)	
Number of patients with bleed, n (%)	x (xx.x)	x (xx.x)	x (xx.x)	
Number of bleeds	х	x	х	
Bleeds per patient (min; max)	x ; x	x ; x	x ; x	
Mean observation period (days)	xxx	xxx	xxx	
Total observation period (days)	XXX	xxx	XXX	
Annualized bleeding rate				
n	х	x	х	
Mean (SD)	x.xx (x.xx)	x.xx (x.xx)	x.xx (x.xx)	
Median	X.XX	x.xx	x.xx	
Min ; Max	x.x ; x.x	x.x ; x.x	x.x ; x.x	

N: Number of patients in Full Analysis Set (FAS). n: Number of patients with the parameter. SD: Standard Deviation. n\*: Number of bleeds.

Severity: Assessment by investigator.

Cohort 1: AAV5-hFIX 5.0 x 10^12 gc/kg, Cohort 2: AAV5-hFIX 2.0 x 10^13 gc/kg

Only bleeds requiring on demand FIX infusion are included.

Total observation period (yrs) for each cohort is calculated as the sum of the observation periods of all patients in that cohort.

	Idlix
Trial ID: CT-AMT-060-01	Final Version 05
EudraCT No: 2013-00557942-42 Table Shells	Page 32 of 66

Table 14.2.17 Summary of post treatment bleeding episodes and annualized bleeding rates - Period: From last prophylactic dose to cut-off - Traumatic bleeds - FAS

	Cohort 1 (N=x) n (%)	Cohort 2 (N=x) n (%)	Total (N=x) n (%)	
Severity, n*				
Severe	х	х	х	
Mild/Moderate	х	х	х	
Location, n*				
Right - Joint, Ankle	х	х	х	
Right - Joint, Elbow	х	х	х	
Right - Joint, Knee	х	х	х	
Right - Joint, Toe(S)	х	х	х	
Right - Muscle, Hip, Leg Or Foot	х	х	х	
Left - Joint, Elbow	х	х	х	
Left - Joint, Knee	х	х	х	
Continued for left	х	х	х	
Muscle, Back Incl Buttocks	х	х	х	

N: Number of patients in Full Analysis Set (FAS). n: Number of patients with the parameter. SD: Standard Deviation. n\*: Number of bleeds.

Severity: Assessment by investigator.

Cohort 1: AAV5-hFIX 5.0 x 10^12 gc/kg, Cohort 2: AAV5-hFIX 2.0 x 10^13 gc/kg

Only bleeds requiring on demand FIX infusion are included.

Total observation period (yrs) for each cohort is calculated as the sum of the observation periods of all patients in that cohort.

 Sponsor: uniQure biopharma B.V
 Date 27MAY2021

 Trial ID: CT-AMT-060-01
 Final Version 05

 EudraCT No: 2013-00557942-42
 Table Shells

 Table 14.2.18 Summary of bleeding episodes and annualized bleeding rates - Unknown bleeds - Period: From tapering-off to cut-off - FAS

As 14.2.17

Sponsor: uniQure biopharma B.V	Date 27MAY2021	larix
Trial ID: CT-AMT-060-01 EudraCT No: 2013-00557942-42	Table Shells	Final Version 05 Page 34 of 66

Table 14.2.19 Summary of bleeding episodes and annualized bleeding rates - Spontaneous and unknown bleeds - Period: From tapering-off to cutoff - FAS

	Cohort 1 (N=x) n (%)	Cohort 2 (N=x) n (%)	Total (N=x) n (%)
Number of patients with bleed, n (%)	x (xx.x)	x (xx.x)	x (xx.x)
Number of bleeds	х	x	х
Bleeds per patient (min; max)	x ; x	x ; x	x ; x
